## 5 Devices

Participants in the intervention group will require the following devices and access requirements:

[figure not shown]
**Table 5:** *Devices required for participants in intervention group*

1	Android based smartphone and/or tablet computer	Preferably participant's own device. Can be supplied by site if participant does not own Android compliant device
2	Internet access – WiFi	Participant's own internet plan and WiFi modem in place of residence.
3	Mobile phone data	Participant's existing mobile phone plan and SIM card with appropriate level of data access
4	Medisana ViFit MX3 wristband	Site to provide one ViFit activity tracking wristband per participant in the intervention group
5	Personal computer (optional)	Participant's own PC can be used an optional additional device for connection to My-AHA portal

## 6 Assessment protocol

### 6.1 Overall Design

The design of the assessment phases is illustrated in Figure 2, with a detailed list of individual measures at each assessment phase described in Table 6.

**Figure 2: Schematic of Study Design**

**Table 6: Assessment battery for the My-AHA RCT assessment points**

DOMAIN	Test name	Screening	Baseline	6mth	12mth	18mth
Consent process	Information sheets and consent forms (Appendix 1, Appendix 2, Appendix 3)	✓ Appendix x 1	✓			
Screening questionnaire	Screening for inclusion and exclusion criteria; including pre-frail assessment	✓				
Demographic	Standard questionnaire 
 
• Date of birth
 
• Gender
 
• Education (years completed)
 
• Residential status (live alone, with other etc.)
 
• Fear of falls
 
• Falls history
 
• Cognitive activities (mental activity)
 
• Medical history (diseases/diagnoses past and current, medication history)
 
• Continence
 
		✓			
	Brief demographic update questionnaire (to track demographic variables than can change over time): 
 
• Change in residential status since prior assessment
 
• Fear of falls
 
• Falls history since previous assessment
 
• Continence
 
• Cognitive activities (mental activity) since previous assessment
 
• Medical since previous assessment point (diagnoses existing and new, medication prescription current)
 
			✓	✓	✓
RCT Adherence	Cognitive games (in My-AHA platform) time spent in game, time scheduled	✓	✓	✓	✓	
	iStoppFalls – time spent/time scheduled	✓	✓	✓	✓	
	FAME – calendar with diary	✓	✓	✓	✓	
	OTAGO – calendar with diary	✓	✓	✓	✓	
	Endurance training (heart rate monitor, calendar with diary)	✓	✓	✓	✓	
	VitalinQ – time spent/recipes used	✓	✓	✓	✓	
	Technology – duration and frequency of app use	✓	✓	✓	✓	
Health	WHO-QoL OLD	✓	✓	✓	✓	
	Lawton-Brody iADL scale	✓		✓	✓	
Physical	Weight (kg)	✓	✓	✓	✓	✓
	Height (cm)	✓	✓	✓	✓	✓
	Grip strength	✓	✓	✓	✓	✓
	CES-D (2 items assessing exhaustion)	✓	✓	✓	✓	✓
	Time to walk 4m (SPPB)	✓	✓	✓	✓	✓
	IPAQ-Short version	✓	✓	✓	✓	✓

	6-minute walk test	✓	✓	✓	✓
	Short Physical Performance Battery (SPPB)	✓	✓	✓	✓
	Dual-Task Performance (repeat of gait speed test of the SPPB)	✓	✓	✓	✓
	Timed up and Go test	✓	✓	✓	✓
	ABC (self-efficacy for physical function)	✓	✓	✓	✓
	PACES (Physical Activity Enjoyment Scale)				✓
Cognitive	MMSE	✓	✓	✓	✓
	HVLT	✓	✓	✓	✓
	WMS-III Spatial Span (SSP)	✓	✓	✓	✓
	Trail Making Test (TMT-A & TMT-B)	✓	✓	✓	✓
	Stroop test (24 item Victoria Version)	✓	✓	✓	✓
	WAIS-III Digit Symbol substitution (DSS)	✓	✓	✓	✓
Psychological	HADS	✓	✓	✓	✓
	LSNS-R (Lubben Social Network Scale, Short form)	✓	✓	✓	✓
Social	UCLA Loneliness Scale	✓	✓	✓	✓
	BMI ( derived from height/weight data in Physical battery )	✓	✓	✓	✓
	Self-MNA	✓	✓	✓	✓
Technology	Evaluation of Usability Scale (SUS)				✓
	DART questionnaire				✓
	Computer Literacy Scale (CLS)			✓	
	User Experience Questionnaire (UEQ)				✓
Measures used to determine pre-frailty status of participants (see Table 2)					
Estimated maximum protocol duration:					

 
• Screening assessment – 60 min (1hr)
 
• Baseline assessment – 155 min (2hr 35min)
 
• 6 month assessment – 130 min (2hr 10 min)
 
• 12 month assessment – 135 min (2hr 15 min)
 
• 18 month assessment – 155 min (2hr 35min)
 
					

## 6.2 Screening questionnaire

Persons expressing an interest in participating in the My-AHA RCT will undergo formal screening to ensure that they meet inclusion criteria and do not meet any of the identified exclusion criteria (see Section 3 Participant Screening, Table 1, Table 2, Table 3, Table 4). A standard questionnaire for participant screening will be used (Appendix 4) along with standard forms for the MMSE, HVLT, IPAQ, and HADS which will be administered to confirm each participant meets pre-frailty criteria for inclusion in the RCT. It is estimated that the screening process will take a maximum of 60 minutes to complete.

## 6.3 Adherence assessment

Adherence to the intervention packages (see Section 6) are recorded automatically through the platform (Section 8). The system records all complete and incomplete sessions of intervention and can confirm whether a scheduled training session has been completed or not, which is then registered in the calendar.

## 6.4 Demographic measures

### 6.4.1 Standard demographic questionnaire

At baseline assessment, all participants will be required to complete the *Standard Demographic Questionnaire* (Appendix 5).

This questionnaire collects information from each participant regarding:

- Date of birth
- Gender
- Education (years completed)
- Residential status (live alone, with other etc.)
- Fear of falls
- Falls history
- Cognitive activities (mental activity)
- Medical history (diseases/diagnoses past and current, medication history)
- Continence/incontinence

### 6.4.2 Brief demographic questionnaire

At follow-up assessment time points (6, 12, 18 months) the *Brief Demographic Questionnaire* (Appendix 6) is to be completed by each participant. This questionnaire is designed to collect data on demographic variables that may change across the duration of the RCT, specifically information regarding changes in:

- Change in residential status since last assessment
- Current fear of falls
- Falls history since last assessment
- Cognitive activities (mental activity) engaged in since last assessment
- Medical since last assessment point (diagnoses existing and new, medication prescription current)
- Continence/incontinence

## 6.5 Health assessment

### 6.5.1 WHOQol-OLD

The *World Health Organisation Quality of Life – OLD extension* (WHOQol-OLD) is a 24-item self-administered scale, assessing quality of life in older adults (Appendix 7).

Responses are recorded on Likert-scaled items assigned to six facets: “Sensory Abilities” (SAB), “Autonomy” (AUT), “Past, Present and Future Activities” (PPF), “Social Participation” (SOP), “Death and Dying” (DAD) and “Intimacy” (INT). Each of the facets has 4 items, thus for all facets the score of possible values can range from 4 to 20, provided all items of a facet have been completed (see **Error! Reference source not found.**). The scores of these six facets or the values of the 24 single items of the WHOQOL-OLD module can be combined to produce a general (“overall”) score for quality of life in older adults, denoted as the WHOQOL-OLD module “total score”. As empirically supported by analyses of the measurement model via structural equation modelling (see below), quality of life is conceived as a higher-order factor, underlying the structure of the WHOQOL-OLD module.

### 6.5.2 Instrumental Activities of Daily Living (iADL)

The *Lawton-Brody Instrumental Activities of Daily Living (iADL)* Scale is an 8-item examiner administered scale, assessing the highest level of functional capacity of the participant across 8 areas of daily activity (Appendix 8):

1. Ability to use a telephone
2. Shopping
3. Food preparation
4. Housekeeping
5. Laundry
6. Mode of transportation
7. Responsibility for own medications
8. Ability to handle finances

## 6.6 Physical assessment

### 6.6.1 Weight

Participants weight (in kg) will be recorded at each assessment point on a standard set of calibrated digital scales. Each site will use the same digital scale for all participants.

Additionally, participants will be screened to ascertain if they meet Fried criteria for weight loss (unintentional) of more than 4.5kg in the preceding 12 months.

### 6.6.2 Height

Participant's height will be measured (in cm) using standardized stadiometer measurements. A stadiometer is constructed from a vertical ruler with a sliding horizontal headpiece which is adjusted to rest on top of the head. Each site will utilise the same stadiometer for all participant assessments at each visit. The stadiometer will be portable to enable assessment visits to occur at the participant's place of residence.

### 6.6.3 Grip Strength

Dominant hand grip strength (kg) is to be assessed using a **Jamar Hand Grip Dynamometer (Model 5030J1)**. The participant is asked to sit upright in a chair without placing his/her forearms on armrests. With dynamometer handle held in their dominant hand., the participant is instructed “to squeeze your hand with all your power, give everything you have.” The examiner will provide verbal encouragement to the participant to squeeze harder during the assessment. The hand dynamometer is to be cleaned with alcohol disinfectant wipes after each participant.

### 6.6.4 Exhaustion (CES-D)

Two (2) items from the CES-D Depression scale will be completed by each participant. Participants respond on a 4-item Likert scale ranging from “rarely or none of the time (less than 1 day)” to “most or all of the time (5-7 days) for how often they have felt the following during the past week (Appendix 9):

Item 7 I felt that everything I did was an effort

Item 20 I could not get “going”.

CES-D Response Key:

Rarely or none of the time (less than 1 day)	Some or a little of the time (1-2 days)	Occasionally or a moderate amount of time (3-4 days)	Most or all of the time (5-7 days)
			

### 6.6.5 IPAQ-short version

The *International Physical Activity Questionnaire (IPAQ)* short form is a standardized and validated self-administered questionnaire comprising 7 items that assess a person's level of physical activity in the preceding 7 days across vigorous, moderate and gentle levels of activity (Appendix 11).

IPAQ scores are converted to a standard energy consumption metric of MET-minutes/week. This metric is then converted to a kilocalorie (kcal) unit of energy expenditure adjusted for the participant's weight using the following formula:

$$\text{kcal} = (\text{Total physical activity MET-min/week}) \times (\text{weight kg}/60)$$

Gender specific cutoff values for PRE-FRAIL are based on kcal cutoffs:

- Men: < 383 kcal
- Women: <270 kcal

### 6.6.6 6 minute walk test

**Description:** The 6-Minute Walk test is a **sub maximal measure of aerobic capacity**. Participants may use an ambulation aid and oxygen if they do so normally. The 6MWT is a useful measure of **functional capacity** suitable for frail older adults. The test has been widely used for preoperative and postoperative evaluation and for measuring the response to therapeutic interventions for pulmonary and cardiac disease.

**Equipment:** pulse oximeter, Blood Pressure cuff, Borg RPE, dyspnea scale, stopwatch, tape measure, portable chair

**Absolute contraindications (test not to be administered):**

- unstable angina during the previous month
- myocardial infarction during the previous month.

**Relative contraindications (test only administered with medical clearance):**

- Resting HR > 120
- SBP > 180 mm Hg
- DBP > 100 mm Hg

**Terminate exercise IMMEDIATELY if and of the following symptoms exhibited:**

Angina, light-headedness, confusion, ataxia, staggering unsteadiness, pallor, cyanosis, nausea, marked dyspnea, unusual fatigue, claudication or other significant pain, facial expressions signifying distress.

Notify treating medical practitioner if test is terminated for any of the above reasons.

## Instructions to the Participant:

"The objective of this test is to **walk as far as possible** for 6 minutes. You will walk back and forth in this hallway. Six minutes is a long time to walk, so maybe you will be exerting yourself. You will possibly get out of breath or become exhausted. You are permitted to slow down, to stop, and to rest as necessary. You may lean against the wall (or at chairs which are places throughout the course) while resting, but resume walking as soon as you are able.

You will be walking back and forth around the cones. You should pivot briskly around the cones and continue back the other way without hesitation. Now I'm going to show you. Please watch the way I turn without hesitation. "We will avoid having a conversation so that you can save your wind for walking. You can begin when I say 'go'.

At the end of the 6 minutes:

- Have participant sit down (portable chair)
- Have patient rate their Borg Rate of Perceived Exertion (RPE), and dyspnea
- Calculate and record the distance walked, as well as the RPE, heart rate and dyspnea values.
- Ask: "What, if anything, kept you from walking farther?"

## Safety:

Monitor vital signs before after the test. If there is an unexpected vital sign response, continue monitoring and documenting every 5 minutes until SBP and HR returns to within about 10-20 of pre-exercise values. Note heart rhythm, especially if it changes from a regular rhythm in pre-exercise to an irregular rhythm in post-exercise.

### **6.6.7 Timed up and go test**

Equipment: arm chair, tape measure, tape, stop watch.

Begin the test with the participant sitting correctly (hips all the way to the back of the seat) in a chair without arm rests. The chair should be stable and positioned such that it will not move when the participant moves from sit to stand. The participant is not allowed to use the arm rests during the sit – stand and stand – sit movements.

Place a piece of tape or other marker on the floor 3 meters away from the chair so that it is easily seen by the participant.

Instructions: "On the word GO you will stand up, walk to the line on the floor, turn around and walk back to the chair and sit down. Walk at your regular pace. (While giving the verbal instructions, the examiner performs the test once himself to ensure the participants understood the task)

Start timing on the word "GO" and stop timing when the participant is seated again correctly in the chair with their back resting on the back of the chair.

---

The participant wears their regular footwear, may use any gait aid that they normally use during ambulation, but may not be assisted by another person. There is no time limit. They may stop and rest (but not sit down) if they need to.

The participant should be given a practice trial that is not timed before testing.

### **6.6.8 *Short Physical Performance Battery (SPPB)***

Equipment required:

- Chair with arms (46-18 cm high)
- Stopwatch
- Tape measure
- tape to mark 4m

SBBP subtests are administered in the following order (Appendix 10).

#### **6.6.8.1 Balance test**

Comprises 3 measures of balance. The examiner provides a verbal instruction with accompanying physical demonstration of the movement to be performed by the participant. If the participant is unable to perform the movement, then the next measure of balance is performed.

The participant must be able to stand unassisted without the use of a cane or walker.

##### **(i) Side-by-Side Stand**

Participant is instructed to stand with feet together (side-by-side) for 10 seconds. The participant may use their arms, bend their knees, or move their body (but not their feet) to maintain balance. Examiner provides sufficient support of the participant's arm to prevent any sudden loss of balance.

If participant passes this test, proceed to test (ii).

If participant unable to pass this test, proceed to test (b – Gait Speed Test)

##### **(ii) Semi-Tandem Stand**

Participant is instructed to stand with one foot in front and side of the other foot, such that the heel of one foot is touching the big toe of the other foot for 10 seconds. The participant may use their arms, bend their knees, or move their body (but not their feet) to maintain balance. Examiner provides sufficient support of the participant's arm to prevent any sudden loss of balance.

If participant passes this test, proceed to test (iii).

If participant unable to pass this test, proceed to test (b – Gait Speed Test)

---

### **(iii) Tandem Stand**

Participant is instructed to stand with one foot in front and side of the other foot, such that the heel of one foot is in front of the other foot and the heel of one foot is touching the toes of the other foot (in a straight line) for 10 seconds. The participant may use their arms, bend their knees, or move their body (but not their feet) to maintain balance. Examiner provides sufficient support of the participant's arm to prevent any sudden loss of balance.

#### **6.6.8.2 Gait Speed Test**

The examiner observes how the participant walks normally. Participant may use a cane or other walking aid if normally used.

##### **(i) First Gait Speed Test**

Participant walks a distance of 4m in a straight line – marked by a tape measure. Examiner demonstrates first, then follows behind the participant as they walk the course. Time to travel 4m is recorded.

##### **(ii) Second Gait Speed Test**

Participant repeats walking a distance of 4m in a straight line – marked by a tape measure. Examiner demonstrates first, then follows behind the participant as they walk the course. Time to travel 4m is recorded.

##### **(iii) Dual-task performance**

Participant repeats walking a distance of 4m in a straight line – marked by a tape measure. However, this time the participant is instructed to count backwards by 7 from 200 while walking (e.g. “200, 193, 186 ....”). The participant counts aloud from when they start walking and stops counting once both feet have crossed the finish line.

#### **6.6.8.3 Chair Stand Test**

Examiner assesses the participant's ability to stand from sitting on a chair and to repeatedly sit-stand-sit.

##### **(i) Single Chair Stand**

Participants is instructed to stand from sitting in a chair. They must keep their arms crossed/folded across their chest from seated to standing position.

If unable to do so, they are instructed to use their arms to stand (do not proceed to next test).

## **(ii) Repeated Chair Stands**

Participants is instructed to stand from sitting in a chair without using their arms, for 5 repetitions as quickly as they can. They must keep their arms crossed/folded across their chest from seated to standing position and from standing to seated position.

### **6.6.9 *The Activities-specific Balance Confidence (ABC) scale***

The ABC is a self-rated 16 item questionnaire in which the participant indicates their level of confidence in doing a physical activity without losing their balance or becoming unsteady from choosing one of the percentage points on the scale from 0% to 100% (Appendix 12).

Where the participant does not currently do the activity in question, they are asked try and imagine how confident they would be if they had to do the activity. If the participant normally uses a walking aid to do the activity or hold onto someone, they are asked to rate their confidence as though they were using these supports.

### **6.6.10 *Physical Activity Enjoyment Scale (PACES)***

The PACES is an 18 item questionnaire asking the participants to respond to questions relating to their enjoyment in undertaking physical activity at the moment (Appendix 13).

Responses are provided on a 7 item Likert scale, with items 1, 4, 5, 7, 9, 10, 11, 13, 14, 16 and 17 being reverse scored (i.e. if participants select 1 score = 7; 2 = 6; 3 = 5; 4 = 4; 5 = 3; 6 = 2; 7 = 1).

Total score is the sum of scores of the 18 items, following reverse scoring of the 11 reversed items. Total score range is 18 – 126.

## 6.7 Cognitive assessment

### 6.7.1 Mini-Mental State Examination (MMSE)

The MMSE is an 11-item brief screening assessment of basic cognitive functions  (Appendix 14). The MMSE is a clinical test, and will be administered by a trained and experienced researcher under the supervision of A/[name], APHRA registered Psychologist endorsed for practice as a Clinical Neuropsychologist.

The 11 items on the MMSE assess:

1. Orientation to time
2. Orientation to place
3. Registration of 3 objects
4. Attention and calculation
5. Recall of 3 objects
6. Language and praxis

Scores on the MMSE range from 0-30, and are corrected for level of education.

Abnormal cutoff scores are:

- < 24 – university/college education
- < 23 – high school education (9-12 years formal education)
- < 21 – junior high school education or less (fewer than 9 years of formal education)

[figure not shown]

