#### **INCLUSION CRITERIA**

---

1. Age: over 60 yrs
2. Familiar with use of smartphones and/or tablet computers
3. Have access to WiFi connection and existing internet data plan and provider
4. Able to stand and walk unassisted
5. Free of significant cognitive impairment (age-corrected MMSE  $\geq 24$ ) (Table 4)
6. Free of clinically significant mood disturbance (HADS-Anxiety  $<15$ ; HADS-depression  $< 15$ ) (Table 4)
7. Free of any acute or unstable medical conditions
8. Meet criteria for pre-frail status (Table 2)
9. Able to understand directions and participate in the protocol
10. Able to sign informed consent

---

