**Table 4: Exclusion criteria for clinically significant deficits in Cognitive and Psychological function**

Clinical sign/symptom		Measure	Cutoff values	
COGNITIVE DOMAIN	Must NOT meet 1 or more of the EXCLUSION CRITERIA		INCLUSION CRITERIA	EXCLUSION CRITERIA
1. Evidence of lowered general cognitive function	Mini Mental State Examination test (MMSE) screens for deficits across several cognitive functions.	Age-adjusted MMSE 
 
• 24-30 (no cognitive impairment)
 
	Age-adjusted MMSE score 
 
• 18-23 = MCI
 
• 0-17 = severe clinical deficit
 
	
2. Evidence of lower than age-appropriate learning and recall of verbal information	Hopkins Verbal Learning Test (HVLT) is a brief test of verbal list learning and memory. Comprises 12 words, organized into three semantic categories, and presented over three consecutive learning trials.	HVLT-total recall score 
 
• Score <math>\geq 25</math>
 
	HVLT-total recall score 
 
• Score <math>\leq 24</math>
 
	
PSYCHOLOGICAL DOMAIN	Must NOT meet any EXCLUSION CRITERIA		INCLUSION CRITERIA	EXCLUSION CRITERIA
1. Increased levels of anxiety and/or lowered mood experienced over the preceding week	HADS – Hospital and Depression Scale, a 14-item scale to which participant indicates degree of agreement/frequency of experience in previous week on a 4 point scale. Seven of the items relate to anxiety and seven relate to depression.	Scores are computed separately for the Anxiety scale (7 items – HADS-a) and the Depression scale (7 items – HADS-d): 
 
0-7 = normal mood
 
8-10 = mild symptoms
 
11-14 = moderate symptoms
 
	
 
• Scores <math>\geq 15</math> - HADS-d and/or
 
• Scores <math>\geq 15</math> - HADS-a
 
	

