**COGNITIVE FRAILTY ASSESSMENT**

1	MMSE Raw Score = _____ / 30	Age-Adjusted Score $\leq$ 26	YES / NO
MMSE Age-adjusted Score = _____ / 30			
2	Hopkins Verbal Learning Test (HVLT)	HVLT total recall score $\leq$ 24	YES / NO
HVLT total recall score = _____ / 36			
TOTAL NUMBER OF “YES”			/ 2
		If 0 YES	Include
		If 1 or 2 YES	EXCLUDE

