### **Interpretation of the MMSE**

Method	Score	Interpretation
Single Cutoff	<24	Abnormal
Range	<21	Increased odds of dementia
	>25	Decreased odds of dementia
Education	21	Abnormal for 8 th grade education
	<23	Abnormal for high school education
	<24	Abnormal for college education
Severity	24-30	No cognitive impairment
	18-23	Mild cognitive impairment
	0-17	Severe cognitive impairment

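### The MMSE entry criterion uses an age-corrected score with no stated rule, while Section 6.7.1 corrects by education with its own cut-offs

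*Protocol*

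**What the plan says.** Three places in the protocol decide entry on the MMSE, and all three refer to age.

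- **Table 1, criterion 5:** "Free of significant cognitive impairment (age-corrected MMSE", with a threshold of at least 24 and a pointer to Table 4.
- **Table 4:** includes an age-adjusted 24-30. Under "Age-adjusted MMSE score" it excludes 18-23 (labelled MCI) and 0-17.
- **Appendix 4, Cognitive Frailty Assessment:** has one field for the raw score and another for "MMSE Age-adjusted Score". It counts an age-adjusted score of 26 or less as a reason to exclude.

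Two places describe a correction by education.

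- **Section 6.7.1:** "Scores on the MMSE range from 0-30, and are corrected for level of education". Abnormal is below 24 for university or college, below 23 for 9-12 years of formal education, and below 21 for fewer than 9 years. Age is not mentioned.
- **Interpretation of the MMSE,** a sheet in the Appendix 4 screening package and again in Appendix 14: gives below 24 for college and below 23 as "Abnormal for high school education". For 8th grade it prints 21 without a less-than sign.

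Years of education are collected on the standard demographic questionnaire at baseline (Section 6.4.1, Appendix 5). The Appendix 4 checklist does not ask for them.

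**The concern.** A screener must turn a raw MMSE into an age-adjusted one, and the readable protocol does not say how. The only correction printed with numbers is by education, and it sits in the same screening package as the age-adjusted field. Someone completing the form could reasonably enter the raw score, apply an age table from elsewhere, or turn to the education cut-offs. These routes can give different eligibility decisions for the same volunteer.

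What is at stake is who enters the trial on a core cognitive criterion, and whether the population can be described reproducibly afterwards. Volunteers with less schooling are the ones for whom Section 6.7.1 and Tables 1 and 4 can disagree.

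**Working it through.** No sample size or power figure is involved, and the plan states no figure to reproduce. The check lists which scores the two descriptions treat differently.

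**Inputs.** Section 6.7.1 cut-offs *c*: 24 (university), 23 (9-12 years), 21 (fewer than 9 years). Entry threshold in Tables 1 and 4: adjusted score at least 24. Checklist trigger in Appendix 4: adjusted score 26 or less excludes. Age adjustment *a*: not given, so it is assumed, over a range of -1 to +3 points added to the raw score.

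**Tables 1 and 4.** A raw score *s* is discordant if it is not abnormal under Section 6.7.1 (*s* ≥ *c*) but excluded on the adjusted score (*s* + *a* < 24). That gives *c* ≤ *s* ≤ 23 - *a*, which is max(0, 24 - *a* - *c*) values.

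| Assumed *a* | Fewer than 9 years | 9-12 years | University |
|---|---|---|---|
| -1 | 21-24 | 23-24 | 24 |
| 0 | 21-23 | 23 | none |
| +1 | 21-22 | none | none |
| +2 | 21 | none | none |
| +3 | none | none | none |

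At *a* = 0 the counts are 24 - 21 = 3, 24 - 23 = 1 and 24 - 24 = 0. For 9-12 years of schooling, 21 and 22 are abnormal in Section 6.7.1 as well, so only 23 is discordant.

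**Appendix 4 checklist.** Exclusion is now *s* + *a* ≤ 26, so the band is *c* ≤ *s* ≤ 26 - *a*. At *a* = 0 this gives 21-26, 23-26 and 24-26, or 6, 4 and 3 values. University education is affected here, although it is not under Tables 1 and 4. Separately from the correction, adjusted scores of 24, 25 and 26 are included by Tables 1 and 4 and excluded by the checklist at every level of schooling.

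**21 against below 21.** If the interpretation sheet's entry is read as making a score of 21 abnormal, the band for fewer than 9 years at *a* = 0 under Tables 1 and 4 is 22-23 rather than 21-23. The two printings of the education cut-offs therefore differ at one score.

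**Where the entry bands come from.** Table 4's bands (24-30, 18-23, 0-17) are the same numbers as the severity bands on the interpretation sheet. The sheet attaches no age adjustment to them; Table 4 does.

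**The case against.** The strongest reply is that Section 6.7.1 describes an instrument and never says its cut-offs decide eligibility. Every place that decides entry uses an age-corrected score, and Section 6.2 sends screening to those tables and to Appendix 4. Being not abnormal on an education norm while failing a stricter entry threshold is not in itself a contradiction. This stands. A reader might infer that Section 6.7.1 is a rival entry rule and that volunteers with less schooling are wrongly excluded. The documents do not support that. What remains is that the entry score has no stated derivation, and the only stated correction of the same test uses another variable.

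It is also fair to say that an age rule might sit in a figure missing from the readable text, and that the interpretation sheet lists a source giving population norms by age and education. The first possibility cannot be excluded. On the second, the norms are not reproduced and no text tells sites to use them.

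A reader might further infer that sites will recruit different populations, or that the comparison of arms is biased. Neither is shown. This protocol recruits 50 participants from one region. Other sites exist, but allocation takes place within each site, so differing site practice on the MMSE would not by itself unbalance the arms.

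Finally, the gap between 24 in the tables and 26 on the checklist may matter more than the choice of correction. That is a reason to settle both together.

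**Conclusion.** The concern holds as an unreconciled scoring rule. Tables 1 and 4 and Appendix 4 require an age-corrected MMSE that cannot be computed from the readable text. Section 6.7.1 and the interpretation sheet correct by education instead, and disagree with each other at a score of 21.

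The size depends on an unstated quantity. With zero age adjustment, which is an assumption, three scores are affected below 9 years of schooling, one at 9-12 years, and none at university level under Tables 1 and 4. It would be tempting to say that raw scores of 21-23 are excluded for everyone with less schooling. That is too broad: the full band applies only below 9 years, and exclusion acts on the adjusted score, not the raw one. The checklist trigger changes the range again.

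The number of volunteers affected is unknown, and the separate HVLT criterion may exclude some of them anyway. The point should be corrected because an entry threshold ought to be computable and the repair is cheap. No bias in the treatment comparison has been shown.

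**What to change.** Reconcile Table 1 criterion 5, Table 4, Section 6.7.1, the Appendix 4 checklist and both copies of the interpretation sheet (Appendices 4 and 14) to one correction and one cut-off.

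- If the correction is by age, print the table or formula, or cite its source, and state what role, if any, the education cut-offs keep.
- If it is by education, resolve 21 against below 21, and record years of education on the Appendix 4 checklist before the eligibility decision.
- In either case, settle the checklist's 26 against the tables' 24 in the same amendment.

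Which correction and which cut-off to use is for the sponsor; the documents support only that they must agree. The cost is amendment wording plus either one printed or cited rule or one extra question at screening. Whichever rule is chosen, some scores now treated differently in different places will change status, so the amendment should say from when it applies.
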